Study Protocol

**Efficacy and Safety of Prophylactic
Treatment for *Pneumocystis Jirovecii*
Pneumonia (PJP) in Patients with
Autoimmune Inflammatory Rheumatic
Disease (AIIRD)**

Version date: 2024.07.04

Background

Pneumocystis jirovecii pneumonia (PJP) is an opportunistic infection that occurs in immunocompromised patients. The typical clinical symptoms include fever, cough, and dyspnea, with a rapid onset and progression to hypoxemia and even respiratory failure. PJP can be divided into HIV-associated PJP and non-HIV PJP [1-2]. In recent years, with the increasing use of iatrogenic immunosuppressants, the incidence of PJP in non-HIV patients has risen, particularly among patients with autoimmune inflammatory rheumatic diseases (AIIRD), such as systemic lupus erythematosus, rheumatoid arthritis, inflammatory myopathies, and systemic vasculitis [3]. The incidence of PJP in AIIRD patients ranges from 0.7% to 2%, significantly higher than in the general population [4]. In addition, AIIRD patients with PJP are prone to progress to respiratory failure, with severe symptoms, poor prognosis and high mortality. Early identification and prophylactic treatment of PJP could improve outcomes and reduce mortality [5].

Currently, identifying PJP in AIIRD patients is challenging due to overlapping clinical features, such as fever and lymphopenia, and the reduced detection rates of Pneumocystis in respiratory specimens due to immunosuppressant use. Early warning based on serological markers offers a new approach for identifying PJP in AIIRD patients [6-8]. Although there are guidelines for preventing PJP in HIV patients, hematologic malignancies, and solid organ transplant recipients [9-10], no consensus guidelines exist for AIIRD patients on immunosuppressive therapy. More clinical evidence is needed to develop evidence-based clinical guidelines for prophylactic treatment of PJP in AIIRD patients.

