This prospective controlled study will use machine learning and other information technologies to analyze clinical data from AIIRD patients. By fitting early clinical indicators (e.g., symptoms, laboratory results) with PJP infection and outcomes, combined with our center's predictive model (combination factor 1 = IgA – IgM × 2.072/1.411) and international consensus and expert recommendations on PJP prophylaxis [11-17], we aim to establish new screening criteria for high-risk populations, and stratified analysis was performed based on risk factors. We'll assess the efficacy

and safety of prophylactic treatment (TMP/SMZ) for PJP in AIIRD patients, explore the AIIRD populations that benefit the most from prophylactic treatment and evaluate the benefit-risk ratio of prophylactic treatment in AIIRD patients, aiming to achieve early identification and guidance for prophylactic treatment, ultimately reducing PJP incidence and improving outcomes in AIIRD patients.

Objectives

1. Develop and validate a predictive model for PJP infection risk in AIIRD patients to facilitate risk stratification, enhanced monitoring, and early prophylactic treatment.
2. Investigate the impact of prophylactic treatment on the incidence and outcomes of PJP in AIIRD patients, evaluating the efficacy, safety, and benefit-risk ratio of prophylactic treatment.

Study design

This study will prospectively collect peripheral blood, respiratory specimens, and clinical data from AIIRD patients, analyze the biological data, establish clinical prediction models, identify high-risk PJP populations among AIIRD patients and administer prophylactic trimethoprim-sulfamethoxazole (TMP/SMZ) treatment. The efficacy and clinical utility of the PJP infection risk prediction model will be validated, and the impact of prophylactic anti-PJP treatment on incidence and outcomes will be explored.

Selection of AIIRD patients

1. Inclusion criteria

- a) Diagnosed with AIIRD according to international classification criteria and receiving corticosteroid or immunosuppressant therapy;
- b) No prior standard PJP treatment, including first-line TMP/SMZ or other

second-line treatments;

- c) Age \geq 18 years;
- d) Informed consent signed for biological sample collection.

2. Exclusion criteria

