- a) Significant health issues, including (but not limited to) the following: Patients with severe liver injury (elevated serum aminotransferase (ALT, AST), more than 5 times the normal value), severe renal insufficiency (GFR < 30mL/min or Scr > 445umol/L), severe myelosuppression (Hb < 65g/L, PLT < 25 \times 10⁹/L or neutrophil < 0.5 x 10⁹/L);
- b) Screening of known when infected with human immunodeficiency virus (HIV), over the past five years with lymphoid tissue proliferative disease or any organ system malignant tumor medical history, history of solid organ transplant patients;
- c) History of sulfonamide allergy or folate deficiency-related megaloblastic anemia;
- d) Pregnant and lactating women;
- e) Any medical or psychiatric condition that the investigator believes would prevent the trial participant from adhering to or completing the study according to the protocol;
- f) Patient refused to comply with the requirements of this study to complete the work.

Sample size estimation

It is expected to prospectively collect a total of 800 patients diagnosed with AIIRD in our hospital. Based on the previous literature and the experience data of our center, there were large differences in some tested indicators in some subgroups. Because involved in machine learning, the required number of samples roughly follows the http://blog.csdn.net/uestc_c2_403/article/details/72859021 url provided by the algorithm, which is about 10 times the number of dimensions + 1. Prospective data expected into the analysis of the parameters/index for 70. Considering that about 10-20% of patients may have missing data in real-world practice, the final sample size

for prospective collection was $70*1.2*10 \approx 800$.

Study process

1. Enrollment criteria and patient recruitment

a) Define enrollment criteria and recruit eligible AIIRD patients.

b) Explain the study purpose and obtain written informed consent.

2. Construct a clinical prediction model and recognize PJP high-risk patients

a) The prediction model was established by combining the developed prediction model (combination factor 1= IgA-IgM \times 2.072/1.411) with clinically recognized risk factors (including long-term use of high-dose corticosteroids, combination of immunosuppressants, and pulmonary diseases).

b) According above criteria, AIIRD patients with high risk or low risk of PJP are recognized.

3. Grouping and Experimental Intervention

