a) Prospectively, we group AIIRD patients into high-risk and low-risk based on the prediction model, and they are further divided into 4 groups according to the intention-to-treat principle: high-risk group 1 (Patients intend to treat with prophylactic TMP/SMZ), high-risk group 2 (Patients intend to treat without prophylactic TMP/SMZ), low-risk group 1 (Patients intend to treat with prophylactic TMP/SMZ), low-risk group 2 (Patients intend to treat without prophylactic TMP/SMZ).

c) Trimethoprim-sulfamethoxazole intervention regimen: TMP/SMZ 480mg po qd (one tablet per day, oral); Treatment time: routine ≥ 28 days (according to the needs of the patient's condition, as well as the patient's tolerance to the drug and the willingness to treat, the clinician will adjust the time).

4. Follow-up and data collection

a) Establish a long-term follow-up to collect each clinical data on a regular basis.

Study visits were set at baseline, 6 and 12 months after the initiation of treatment. The

end points of follow-up were PJP infection, occurrence of serious side effects, death, loss to follow-up, end of follow-up, or withdrawal from the study. Main outcome indicator is pneumocystis infection incidence, and secondary indicators include TMP/SMZ related adverse events, PJP related mortality, other prognostic indicators and parameters of the respiratory system.

5. Statistics and data analysis

- a) Using difference test statistical analysis methods such as comparing two main outcome indexes between the groups of patients. Possible confounding factors, such as age, gender, and baseline conditions, were considered in the analysis, and covariates were adjusted if necessary.
- b) Statistical analysis methods (such as ROC curve, calibration plot, DCA curve, etc.) were used to evaluate the prediction model performance and visual display (Nomogram, etc.).
- c) Stratified according to risk factors, the absolute risk difference of PJP between the control and prevention groups was calculated, and the NNT was calculated based on the risk difference. The bootstrap method is used to estimate NNT and NNH 95% confidence interval (95% CI), for different people to undergo preventive SMZ/TMP risk-benefit assessments.

Possible risks and preventive measures

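### Section 5c gives a risk difference and NNT within each risk-factor stratum, but nothing that compares strata, although one aim is to find who benefits most

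*Protocol*

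**What the plan says.** The Background states a comparative aim: to "explore the AIIRD populations that benefit the most from prophylactic treatment". Study process, section 5, item c is the only analysis that serves it. It says "Stratified according to risk factors, the absolute risk difference of PJP between the control and prevention groups was calculated", derives the NNT from that difference, and takes bootstrap 95% intervals for NNT and NNH. The stated purpose is "for different people to undergo preventive SMZ/TMP risk-benefit assessments".

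Section 3a forms two risk groups from the prediction model and splits each by intended prophylaxis; patients there are described this way: "they are further divided into 4 groups according to the intention-to-treat principle". Item 5c does not say that these risk groups are its strata. It refers to risk factors, and section 2a lists several: "including long-term use of high-dose corticosteroids, combination of immunosuppressants, and pulmonary diseases", alongside combination factor 1.

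Item 5a adds an unspecific difference test between groups, with covariates adjusted if needed. It names no comparison of the prophylaxis effect between strata.

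**The concern.** Whether one population benefits more than another is a question about the difference between two effects. Item 5c estimates each effect separately and stops there. A reader of the results will have a column of NNTs, each with its own interval, and no measure of whether the differences in that column exceed chance.

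This matters because PJP is rare. With a handful of cases per stratum, an NNT can halve, double or become undefined when one or two cases move. The Background also promises guidance for prophylactic treatment, so a chance ranking could become advice on who should or should not receive it.

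**Working it through.** **The plan's own figure.** The protocol gives no precision or power figure for this analysis. Its sample size is 800, written as 70 × 1.2 × 10. That product is 840; the discrepancy has no bearing here.

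**Inputs from the protocol.** N = 800 ("It is expected to prospectively collect a total of 800 patients diagnosed with AIIRD in our hospital"). Incidence 0.7% to 2% ("The incidence of PJP in AIIRD patients ranges from 0.7% to 2%, significantly higher than in the general population").

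**Assumptions, not in the protocol.** 400 patients with and 400 without prophylaxis; 85% protection (relative risk 0.15) unless stated; binary factors with 50% prevalence that are unrelated to risk and effect; no confounding.

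**Expected cases.** If nobody were treated: 800 × 0.007 = 5.6 and 800 × 0.02 = 16. In one untreated cell of 200: 1.4 and 4. In one treated cell of 200: 0.15 × 1.4 = 0.21 and 0.15 × 4 = 0.6.

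**Chance differences when the truth is identical.** Binomial simulation, 100,000 studies per setting. In each stratum RD = (untreated cases / untreated n) − (treated cases / treated n), and NNT = 1/RD. A study is counted if the two NNTs differ at least twofold, or if RD is zero or negative in one stratum or both.

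| Untreated risk | NNT gap of twofold or more | Benefit in one stratum only | Benefit in neither | Total, one factor | Any of three factors |
|---|---|---|---|---|---|
| 0.7% | 22% | 41% | 8% | 71% | 94% |
| 2% | 38% | 10% | 0.3% | 48% | 82% |
| 5% (sensitivity) | 24% | 0.6% | 0% | 25% | 55% |

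With relative risks from 0.1 to 0.5, and not counting studies with no benefit in either stratum, one factor gives 62-67% at 0.7% and 44-66% at 2%. Three factors give 79-92% over both incidences.

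**Do separate intervals protect?** Wald intervals for RD were used in place of the bootstrap. With identical true effects, one stratum's 95% CI excludes zero and the other's does not in 46% of studies at 2% and 8% at 0.7%.

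**Direct contrast.** Take RD₁ − RD₂ and claim a difference only if its 95% CI excludes zero. For one factor the false-claim rate is 3.4% at 0.7% and 4.9% at 2%. If three factors are each tested, at least one false claim occurs in 9% and 14%.

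**Precision of the contrast.** With 200 per cell, relative risk 0.3 and equal true risk, the half-width is 1.96 × √(2 × [p(1−p) + 0.3p(1−0.3p)] / 200).
- p = 0.02: 1.96 × √(2 × (0.0196 + 0.005964)/200) = 3.1 percentage points, against a true RD of 0.7 × 2% = 1.4 points.
- p = 0.007: 1.9 points, against a true RD of 0.49 points.

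**Power for a real difference.** Untreated risk 2% v 0.7%, relative risk 0.3, 200 per cell. Difference in RD = 0.7 × (0.02 − 0.007) = 0.0091. SE = √((0.0196 + 0.005964 + 0.006951 + 0.002096)/200) = 0.0132. The ratio is 0.69, so two-sided power is about 10%. The true NNTs are 1/0.014 = 71 and 1/0.0049 = 204, yet the low-risk stratum shows the larger RD in 19% of studies.

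**Empty cells.** With 200 per cell, the chance that at least one of the two treated cells has no case is 1 − [1 − (1 − 0.15p)²⁰⁰]². This is 96% at 0.7% and 80% at 2%.

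**The case against.** The strongest reply is that a contrast between subgroup effects is ordinary SAP content, and that a stratum risk difference, an NNT and a bootstrap interval are all valid quantities. The second half is true. But the protocol does not leave the method open: it fixes the effect measure, its transformation, the stratification and the interval, and that set cannot answer its own comparative aim.

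Several further points stand and limit the finding:

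- A reader might infer that the protocol directs the strata to be compared by eye. It says no such thing. Its stated use is risk-benefit assessment, which can be read as NNT against NNH within one population. The point is only that nothing else serves the comparative aim.
- A reader might take the ranking of populations to be the study's main clinical message. The aim is worded as exploratory, stands in the Background, and is repeated in neither numbered objective.
- Stratifying by risk factors may mean the two groups of 3a, since those are partly built from the same factors. Then the one-factor figures apply, and at 2% that is about an even chance.
- The simulated factors carry no risk, whereas the protocol's are recognised risk factors. With a constant relative effect, absolute benefit differs with baseline risk, so some observed NNT differences will be real.
- The root problem is few events. A contrast does not create information; it shows how little there is.

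**Conclusion.** The concern holds in a limited form. Item 5c produces stratum-specific results and no comparison between strata. At the protocol's own incidence, large differences in apparent benefit arise by chance in roughly half to seven-tenths of studies for one factor, and in more than four-fifths for three. The planned separate intervals do not prevent a misreading.

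These rates assume equal arms, 85% protection, 50% prevalence and identical true risk. They fall to about 25% for one factor if the enrolled patients' risk is 5%. It would therefore be too strong to say that chance will usually produce a false difference whatever the strata: for a single split at 2% with a strong effect it is about one in two.

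Nor do the figures support replacing 5c with an ordinary interaction model, because a treated cell is empty in most studies at 0.7-2%. Deriving NNTs from one common relative effect is no cure either. The share of studies with an artefact in any of three factors falls only from 94% to 92% at 0.7%, and from 82% to about 73% at 2%, because the stratum's untreated risk still rests on the same few cases.

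**What to change.** Amend 5c as follows.

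1. Name the high-risk and low-risk groups of 3a as the main strata.
2. Report the difference between their two risk differences with a 95% CI, by bootstrap or another method suited to sparse data.
3. State that one population will be said to benefit more only if that interval excludes zero.
4. Label strata formed by single risk factors as exploratory.
5. If wanted, give NNTs derived from a common relative effect as a sensitivity analysis only.

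For the one main contrast, the false-claim rate is then about 3-5%. It returns to about 9-14% if three factors are each tested, which is why the main contrast should be single.

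The cost is a few lines of text and a little programming. The real downside is low power: about 10% in the 2% v 0.7% example. The contrast will mostly show that these data cannot rank the strata, and fewer statements about who benefits most will be possible.

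### The bootstrap interval behind the stratum NNT fails when a stratum has no untreated PJP case: a 24-33% chance per stratum at 0.7% risk, 2-4% at 2%, under assumed equal groups

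*Protocol*

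**What the plan says.** Item 5c of the Protocol's Study process works within risk strata: "the absolute risk difference of PJP between the control and prevention groups was calculated, and the NNT was calculated based on the risk difference". It then names the interval method: "The bootstrap method is used to estimate NNT and NNH 95% confidence interval (95% CI"). It does not say which type of bootstrap is meant, whether the RD or the NNT is resampled, or what happens when a group has no case.

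The comparison is between treated and untreated patients within the high-risk and low-risk strata. On these groups, item 3a says that "they are further divided into 4 groups according to the intention-to-treat principle". They are formed by intended treatment, not by randomisation. Item 5a allows for adjustment: "Possible confounding factors, such as age, gender, and baseline conditions, were considered in the analysis, and covariates were adjusted if necessary".

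The result carries weight because the Background states an aim to "explore the AIIRD populations that benefit the most from prophylactic treatment", and the stratum NNT is the quantity in the plan that answers it.

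**The concern.** PJP is rare, the sample is split four ways, and a low-risk stratum is constructed on purpose. An untreated group with no PJP case is therefore a realistic outcome. An ordinary bootstrap draws from the observed patients, so a group with no case shows none in every resample and adds no variance.

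The interval then has no room on the benefit side exactly where the data say least. A 0-to-0 result may be noticed. An interval of -1.5% to 0 looks ordinary, yet it excludes any benefit of prophylaxis in that stratum. A benefit-risk statement for low-risk patients could rest on it.

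**Working it through.** **Inputs from the Protocol.** Sample size estimation: "It is expected to prospectively collect a total of 800 patients diagnosed with AIIRD in our hospital", and "Considering that about 10-20% of patients may have missing data in real-world practice". Background: "The incidence of PJP in AIIRD patients ranges from 0.7% to 2%, significantly higher than in the general population". The Protocol states no precision or zero-event figure for the NNT, so there is none to reproduce. (Its sample-size product, 70 × 1.2 × 10, is 840 rather than 800. At 840/4 = 210 per group the 24.5% below becomes 22.9%, so this does not matter here.)

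**Assumptions.** Four equal groups: 800/4 = 200, or 200 × 0.8 = 160 after 20% loss. Untreated risk equal to the overall incidence in both strata, at 0.7% and at 2%. Risk under prophylaxis 0.1, 0.2 or 0.5 of the untreated risk. Expected untreated cases per stratum run from 160 × 0.007 = 1.1 to 200 × 0.02 = 4.

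**Step 1: chance of no untreated case.** For one stratum this is (1 - p)^n. For at least one of two strata it is 1 - (1 - (1 - p)^n)².
- p = 0.7%: 0.993^200 = 24.5% and 0.993^160 = 32.5%. For either stratum: 1 - 0.755² = 43% and 1 - 0.675² = 54%.
- p = 2%: 0.98^200 = 1.8% and 0.98^160 = 3.9%. For either stratum: 3.5% and 7.7%.

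**Step 2: what the bootstrap returns.** Resample each group separately, so that each group's case count is binomial with n and its observed proportion. Take the 2.5th and 97.5th percentiles of RD = untreated minus treated. With 200 per group:

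| Cases, untreated v treated | Bootstrap RD interval | Miettinen-Nurminen |
|---|---|---|
| 0 v 0 | 0 to 0 | -1.89% to 1.89% |
| 0 v 1 | -1.5% to 0 | -2.78% to 1.39% |
| 4 v 1 | -0.5% to 4.0% | -0.97% to 4.59% |

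At 0 v 0 every resampled NNT is 1/0, although the data still allow an RD of 1.89% (NNT 1/0.0189 = 53). At 0 v 1 no resample shows benefit.

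**Step 3: coverage per stratum.** Sum the binomial probabilities of all tables whose interval contains the true RD (exact enumeration, n = 160 to 200, all three risk ratios).

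| Untreated risk | RD bootstrap | Miettinen-Nurminen |
|---|---|---|
| 0.7% | 65-75% | 98.9-99.8% |
| 2% | 85-96% | 93.8-97.1% |

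At 0.7%, 24.5-32.5% of intervals lie wholly below the true RD and 0.1-2.8% lie above it. Given at least one untreated case, coverage is 96-99.9%, so almost all of the shortfall comes from the zero-case tables. At 2% coverage moves irregularly with the exact group size (2% v 0.4%: 93% at 160, 88% at 190, 89% at 200). There, zero untreated cases explain only part of the shortfall.

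**Step 4: unequal risk.** Suppose equal strata with three quarters of cases in the high-risk one.
- An overall 0.7% becomes 1.05% and 0.35%. The low-risk stratum has no untreated case with probability 50-57%, and coverage there is 43-50%. At least one of the two strata is affected with probability 56-65%.
- An overall 2% becomes 3% and 1%, with coverage 91-96% and 76-86%.

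**Step 5: unequal groups.** At 0.7%, the chance of no untreated case in one stratum is 49.5% with 100 untreated and 6.0% with 400. With 100 untreated and 300 treated, coverage is 50% at 0.7% and 86% at 2%. With 300 and 100 it is 86% and 92-94%.

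**The case against.** The strongest reply is that the inputs are not the Protocol's. It sets no group sizes and no stratum risks. Its 0.7-2% is for AIIRD patients overall, whereas everyone enrolled is on corticosteroids or immunosuppressants. Its 10-20% is missing data in a machine-learning sample-size rule, not loss of the PJP outcome. This stands: the percentages are conditional on assumptions, and Step 5 shows how far they move.

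A second reply is that bootstrap type and a zero-event rule commonly belong in the SAP, which is not shown. Their absence is indeed no fault in itself. But the Protocol does fix the bootstrap, and ordinary resampling of patients cannot supply missing cases whichever variant is chosen. A parametric or model-based bootstrap might behave differently. It was not tested, and the text does not name one.

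Third, the gain is limited. Miettinen-Nurminen intervals include zero about as often as the RD bootstrap (59-90% of strata at 2%, 95-98% at 0.7%). Open-ended NNT intervals are therefore mostly a result of few events. This also stands: the change corrects the limits and does not add precision.

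Three stronger readings are tempting. A reader might take 24-33% as the share of studies affected, but it is the chance for one given stratum; for either of two strata it is 43-54%. A reader might say that the NNT interval is falsely narrow, but that is true of the RD interval only; the NNT interval is undefined or has no benefit side. A reader might conclude that the method fails across the stated incidence range, but at 2% the fault is modest.

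**Conclusion.** The point holds in limited form. The Protocol names a method that gives a degenerate or one-sided RD interval, and hence no usable NNT interval, whenever a stratum has no untreated case. The mechanism needs no assumption; its frequency does. With equal groups and the overall incidence as untreated risk, the problem is serious at the low end of the Protocol's range and small at the high end. It is worst in a low-risk stratum, where the plan most needs to tell little benefit from little information. It deserves correction, but it concerns a supporting benefit-risk analysis and not the main comparison of PJP incidence. The NNH interval is not judged here, because the Protocol gives no adverse-event rate.

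**What to change.** In item 5c, for each stratum's crude comparison, replace the bootstrap interval for the NNT with a prespecified Miettinen-Nurminen score interval for the RD. Invert its limits. When the RD interval includes zero, write the result as NNTB ... infinity ... NNTH (number needed to treat for one patient to benefit, through infinity, to number needed for one to be harmed).

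If a covariate-adjusted RD is also reported under 5a, bootstrap on the RD scale only. Where either group has no PJP case, show the crude RD with its score interval, labelled unadjusted, in place of the bootstrap interval.

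The cost is one or two sentences and no extra patients or data. Intervals become wider, are often open-ended, and are somewhat conservative at 0.7%. Under the same assumptions the zero-case fallback would apply in 15-74% of strata at 2% and 62-93% at 0.7%, so an adjusted interval will often be unavailable. The crude interval does nothing about confounding from non-random treatment choice, and the report should say so beside it.
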